## D. 3. Combined Baseline Visit 2/3 for Thresholds' Clients (completed at Northwestern University or at Threshold's location) will require participants to complete:

1. Employment History Interview (EHI) The EHI will assess competitive work history data: length of time since last full-time (or any) employment, number of days employed in the past 5 years, history of prior interview training, and number of job interviews completed in the past three months. The EHI will also assess current housing status, income, and criminal justice history.

2. Brief Psychiatric Rating Scale (BPRS) (lasting approximately 30 minutes). The BPRS will assess psychiatric symptoms including somatic concern, anxiety, emotional withdrawal, conceptual disorganization, guilt feelings, tension, mannerisms and posturing, grandiosity, depressive mood, hostility, suspiciousness, hallucinatory behavior, motor retardation, uncooperativeness, unusual thought content, blunted affect, excitement, and disorientation.

3. The Beck Depression Inventory (approximately 15 minutes) is a self-report of depression symptoms.

A rating of "2 ("I would like to kill myself," or 3 ("I would kill myself if I had the chance" on item 9 on the Beck Depression Inventory indicates presence of suicidal ideation.

When a participant meets one of the above cutoff scores, the research staff will administer the **Columbia-Suicide Severity Rating Scale (C-SSRS).** A total score of 4 or higher on the "Intensity of Ideation" section of this measure will indicate whether or not the participant has a level of suicidal risk that requires further consideration. The procedures outlined in section 10 (Risks to Participants) will be followed if a participant scores 4 or higher.

4. MATRICS Consensus Cognitive Battery (MCCB) (approximately 1 hour) . The MCCB is a standardized cognitive battery for use with adults with schizophrenia and related disorders.

5. Participants will receive a break and be provided a healthy snack.

6. WHO Quality of Life-BREF (WHOQOL-BREF) (approximately 10 minutes) . The WHOQOL-BREF is a brief quality of life survey.

7. The 12-item Short Form Health Survey (SF-12) (approximately 10 minutes) . This assessment is a brief survey about the participant's physical health.

8. Social Skills Performance Assessment (SSPA) (approximately 15 minutes) to assess social competence. Participants will complete two video-recorded roleplays with a research assistant.

9. Baseline Job Interview Role-Play Assessments (approximately 90 minutes): The participant will complete a typical job application, select two fictional job openings (listed below), and participate in two job interview roleplays with two trained role-play interviewers. The interviews will be videorecorded and the videos will be scored by student raters trained to a high standard of reliability and who are blinded to condition. Participants will select two jobs from the following scenarios:

1) Scenario A: The department of Public Health at the University of Illinois at Chicago is running a nation-wide study examining the effects of a newly implemented youth exercise program in elementary schools across the country. We are hiring a team of research assistants to collect and manage our study data. We look forward to building a talented team and have position openings in the following categories: Data Entry Technician, Research Assistant, and Study Coordinator. Position to which they are applying is Data Entry Technician.

**2)** Scenario B: Goldberg & Jones is a new law firm opening in downtown Chicago. G&J is a promising new law firm founded by two law students who recently graduated from Kent Law School. G&J is looking for a dedicated staff to ensure the new law firm's success. Goldberg & Jones are seeking to hire individuals for the following positions: Administrative Assistants, Mail Clerks, and Paralegals. Position to which they are applying is Mail Clerk.

**3)** Scenario C: Lakeview Hospital has provided quality care and treatment to Chicago for the past 50 years. Lakeview Hospital is currently seeking individuals to add to their dedicated team of employees for the following positions: Medical Records Clerk and Medical Receptionist. Position to which they are applying is Medical Records Clerk.

**4)** Scenario D: Goldberg & Jones is a new law firm opening in downtown Chicago. G&J is a promising law firm founded by two law students who recently graduated from Kent Law School. G&J is looking for a dedicated staff to ensure the new law firm's success. Goldberg & Jones are seeking to hire individuals for the following positions: Administrative Assistants, Mail Clerks, and Paralegals. Position to which they are applying is Paralegal.

**5)** Scenario E: Stop & Shop is the second largest, nation-wide supermarket chain. We are opening a new store to sell food and household goods. We look forward to building a talented team and have position openings in the following categories: Customer Service, Cashier, Stock Clerk and Inventory. Position to which they are applying is Inventory Manager.

**6)** Scenario F: At T&C Home Goods, we are committed to quality - both in the value of our product line and in the talent employ. We offer a personalized work environment to hundreds of dedicated associates, with all the perks of a multi-million-dollar company. We offer an extensive selection of home décor and building supplies. Position to which they are applying is Sales Associate.

**7)** Scenario G: Stop & Shop is the second largest, nation-wide supermarket chain. We are opening a new store in Park Ridge, IL to sell food and household goods. We look forward to building a talented team and have position openings in the following categories: Customer Service, Cashier, Stock Clerk and Inventory. Position to which they are applying is Stock Clerk.

**8)** Scenario H: The Cook County Public Library enables researchers, students, teachers, and others to have access to the records of Illinois' past while preserving irreplaceable historical materials for future generations. The sizeable collection of books, journals, manuscripts, newspapers, maps, and prints, available to the public makes it the most frequented library in all of Illinois. Position to which they are applying is Reference Librarian.

Participants will be given an instruction card that corresponds to their selected job scenarios, which is presented below.

**Instructions**: [fill in company name and details] is interviewing for part-time workers, 25 to 30 hours per week. Starting pay is \$15.00/hour. You are interviewing for part-time work, particularly because you need to have Thursdays off for personal reasons. You will need to negotiate for a schedule that will accommodate for Thursdays off.

10. Specific Levels of Functioning (SLOF) Assessment is a 30-item measure that assess one's functioning in the community (approximately 10 minutes).

Combined Visit 2/3 (Pre-test visit) will last approximately 210 minutes or 3 hours and 30 minutes. Participants will be paid \$70.

**D. 4. Randomization for Thresholds' Clients.** After the video-recorded pre-training role-play interviews are completed, participants will be randomized into the intervention group or the wait list control group. Block randomization tables will be created prior to the study based on computer generated blocks of six. Blocks of six will ensure nearly equal groups. Sealed envelopes containing the randomization by sequential subject entry number will be created and stored, and then opened when a participant has completed pre-randomization procedures.

**D. 5. Visits 4-9, Virtual Reality Job Interview Training Delivery.** Participants randomized to the VR training group will complete their VR training at local Thresholds location (see Appendix A), or if requested by the member (at their home). After members have completed their VR-JIT orientation and have demonstrated independence at using VR-JIT with minimal support from staff and completed at least 10 virtual interviews in lab, then study team will support the member to use VR-JIT at home if home use is requested by the member. To provide this support, the research team will show the member how to access the tool in the lab. Moreover, the member will be instructed to call the research team so that the research team can walk the member through accessing the tool once they are at home. In addition, the research team will provide the member with a instructional document so that they can access the tool from home.

The Thresholds Research Coordinator will schedule the study participants to complete 6 two-hour sessions of VR. When participants show up for the VR training, the visit will be run the Thresholds research staff who will provide the trainee with an initial orientation to VR and then monitor the trainee's access and performance scores during the sessions. After completing the initial 6 visits, trainees will move on to complete their post-test visit. Trainees will be invited to use VR as-needed after completing the post-test visit, which will be monitored by the Team Leaders. Those participants assigned to the SE as usual group will have the option to use the VR training in the context of their regular use of Thresholds services (i.e., they will not have access to the study resources to use VR) following the completion of their participation in the study (after their 9-month follow-up phone call). At each training session, any subject who has had to travel to use the intervention will receive \$10 to reimburse them for the cost of transportation.

A note on VR delivery procedures (1/29/18): When the study initially began, Employment Specialists and Team Leaders were asked to run the VR orientation and training sessions. Due to workload expectations and coordination barriers, this responsibility was moved to the Thresholds Research Team.

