### D. Study Procedures for Community Effectiveness Randomized Controlled Trial

D. 1.a. Thresholds research staff will prescreen members using Electronic Health Record (EHR) information. Thresholds research staff will sit in on weekly case coordination visits with Employment Specialist (ES) to discuss members who may be a good fit for the study. If the member agrees, the ES will talk directly with the member to explain the study and see if he/she is interested. The ES may use a recruitment video at this time. Once interest is established, Thresholds research staff will reach out to the client directly via phone. The Thresholds research staff member will use the study screening form to determine the client's initial eligibility for study participation, and then schedule a baseline visit. Screening data collected from individuals who are ineligible or decline participation will be kept on file during the duration of the recruitment period in case eligibility criteria changes then this information will be destroyed after recruitment is completed.

D.1.b. The Thresholds Employment Specialist identifies members who are eligible for research participation base on member's enrollment and employment status. The Employment Specialist give members' information about the research study using the kickoff meeting recruitment script and kickoff meeting recruitment handout, and lets the member know that they may be eligible for the study. The Employment Specialist asks members if they would be interested in learning more about the study at a kickoff meeting with the research team. The kickoff meeting will be a two-hour period at a Thresholds location in which the interested member will have the option to talk to the Thresholds research team. The member will also have the option to talk to the Thresholds' research team via phone instead of attending the kickoff meeting. The Thresholds research team may use the Molly information video during the kickoff meeting. Once interest has been established in joining the study, the Thresholds research staff member will use the study screening form to determine the client's initial eligibility for the study participation, and then schedule a baseline visit. Screening data collected from the individuals who are ineligible or decline participation will be kept on file during the duration of the recruitment period in case eligibility criteria changes. Then this information will be destroyed after recruitment is complete.

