Data Analysis Plan for Aims 1 & 2. In this intent-to-treat study, we will collect data on 160 subjects. The biostatistician will monitor the data for distribution normality and transform abnormally distributed variables if needed. Correction for Multiple Comparisons: To minimize spurious findings, we will adjust the 3 primary tests using a false discovery rate at 0.05 (see below). Covariates: Although randomization should protect against group differences, we will covary for any between-group differences that are observed regarding demographic, cognitive, clinical and vocational history, booster sessions, and the number of completed interviews. Missing Data: We will follow the intent-to-treat principle and in longitudinal analyses we will use multiple imputation models to analyze the data in the presence of missing data. Data processing and cleaning will occur during the study, including checking for missing data and inconsistencies. All videos will be stored on the project's secure server. A Data Safety and Monitoring Board will monitor for adverse events (see 15.0 below).

**Hypothesis 1:** IPS+VR trainees will have higher employment rates than IPS Only by T3. **To test H1**, we will use multiple logistic regression and a Wald Chi-square test of the coefficient to its standard error, to compare the adjusted employment proportions in the two conditions (attained a job=1 vs. failed to attain a job or censored with a job=0, between T1 and T3). We calculated power using simulation in R, correcting for small samples and multiple testing with false discovery rate for the 4 primary tests (our power analysis is conservative, relying on Bonferroni corrections for all tests). Accounting for 10% missing, our trial that recruits 80 subjects in each arm has 80% power for a two-sided 0.05/4=.0125 level test when the OR = 3.2, with IPS+VR effectively doubling the

rate from 25% to 53% employment. Based on our earlier study where we found an OR of 8.7, or effectively tripling the employment rate from 25% to 75%, and a power of 0.99 at this magnitude of effect, we feel confident that we will have sufficient power in this study.

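### A single block size of six is printed in the protocol and one staff group both screens clients and runs VR, so up to a quarter of allocations could be deduced at envelope opening

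*Combined protocol and SAP*

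**What the plan says.** **Allocation.** Section 4.0 D.4 has the randomization tables drawn up before the study from "computer generated blocks of six". The stated purpose is balance: "Blocks of six will ensure nearly equal groups". On concealment it says "Sealed envelopes containing the randomization by sequential subject entry number will be created and stored", each to be "opened when a participant has completed pre-randomization procedures". It gives no stratification factors, no variation in block size, no custodian or opener of the envelopes, and no step to keep the block size from site staff. The ratio is not written out. Section 14.0 (H1) implies 1:1 through "our trial that recruits 80 subjects in each arm".

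**Recruitment.** Section 4.0 D.1.a says "Thresholds research staff will prescreen members using Electronic Health Record (EHR) information". The same staff attend weekly meetings with Employment Specialists to discuss which members would suit the study, apply the screening form and book the baseline visit. D.2 has research staff complete the eligibility checklist.

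**Delivery.** Section 4.0 D.5 says that when participants attend for VR, "the visit will be run the Thresholds research staff". A note dated 1/29/18 records that this task moved to the Thresholds Research Team from Employment Specialists and Team Leaders. Section 16.0 adds that all research staff are cross-trained in every part of the study.

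**Blinding.** Section 4.0 B calls the trial single blinded. The only people named as blinded are the role-play video raters (D.3).

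**The concern.** Sealed envelopes hide the next card. They do not stop someone from deducing it from earlier cards when the block length is fixed and known. The group that delivers VR sees which randomized clients are in the VR arm and can infer which are not. The same group takes part in judging who suits the study and in scheduling visits, so it has some influence over who is brought forward and when.

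If more job-ready clients were brought forward when a VR slot was expected, the arms would differ at baseline in ways that affect employment by T3 (H1) and time to employment (H3). Opening the envelope late prevents changes after the assignment is seen. It does not prevent choices made in anticipation of it.

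**Working it through.** The plan gives no predictability figure, so there is none to reproduce.

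**Inputs.** Block size 6 (4.0 D.4). Ratio 1:1, hence 3 + 3 per block (inferred from equal arms in 14.0). One sequence (assumed, as no strata are given). Sample size 180 (3.0) or 160 (14.0). Control employment rate 25% and 10% missing (14.0, H1), which leaves 80 × 0.9 = 72 analysed per arm.

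**Step 1: certain allocations.** A 3 + 3 block has C(6,3) = 20 equally likely orders. A position is certain if all remaining slots belong to one arm.
- Positions 1 to 3: never.
- Position 4: the last three are alike, 2/20 = 10%.
- Position 5: the last two are alike, 2 × C(4,1)/20 = 8/20 = 40%.
- Position 6: always, 100%.

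Expected certain slots per block = 0.10 + 0.40 + 1.00 = 1.5, and 1.5/6 = 25%. The closed form 1/(m + 1) with m = 3 agrees. This is about 0.25 × 160 = 40 or 0.25 × 180 = 45 clients.

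**Step 2: best guess.** Guess the arm with more slots left, and toss a coin when they are equal. Success by position is 50%, 60%, 60%, 70%, 70% and 100%. These sum to 4.1 correct per block, and 4.1/6 = 68.3%. Unrestricted randomization gives 0% certain and 50% by guessing.

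**Step 3: varying the block size.** I simulated sequences of 180 against a guesser who knows the set of sizes and all earlier assignments, but not the order of the sizes.

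| Block sizes | Certain | Best guess correct |
|---|---|---|
| 6 only | 25% | 68% |
| 4, 6 | 5-6% | 69% |
| 2, 4, 6 | 4% | 70% |
| 4, 6, 8 | about 2% | 68% |
| 6, 8, 10 | about 1.5% | 66% |

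Varying the size removes most of the certainty but hardly changes the best guess.

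**Step 4: what steering could do (illustration on my own assumption).** Suppose that at every certain slot the client's job rate is d points above 25% if the slot is VR and d points below if it is control, with no true VR effect. The arm rates become 25% ± 0.25d, so the bias in the difference is 0.5d. The chance of a false finding in favour of VR (normal approximation, 72 per arm) is:

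| d (points) | Bias (points) | Two-sided 0.05 | Two-sided 0.0125 |
|---|---|---|---|
| 0 | 0 | 2.5% | 0.6% |
| 5 | 2.5 | 5% | 1.6% |
| 10 | 5 | 10% | 3.5% |
| 15 | 7.5 | 18% | 7% |
| 20 | 10 | 28% | 13% |

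Steering at every certain slot is an extreme case. Nothing in the documents gives a value for d or suggests that steering took place.

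**The case against.** A reader might infer that a quarter of allocations are in fact known in advance, or that H1 and H3 are biased. The documents support neither.

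- **The 25% is a ceiling.** It needs knowledge of the block boundaries and all earlier assignments, in a single 1:1 sequence. The staff are named as a group, consent takes place at five Thresholds locations (8.0 A), and nothing says that any one person tracks the sequence. This stands, and it limits the claim to an opportunity.
- **Timing separates screening from allocation.** Two visits of about 3.5 hours each (D.2, D.3) come between screening and envelope opening, and envelopes follow entry number. With several clients waiting, a recruiter at first contact cannot be sure which slot a client will take. This also stands: the figures apply at opening and are lower at screening.
- **Staff are not the only gatekeepers.** Employment Specialists make the first approach (D.1.a, D.1.b). The entry criterion on planned interviews is the client's own report (3.0), so it is weak evidence of staff discretion. The suitability discussions and visit scheduling are better evidence.
- **Eligibility already comes first.** The checklist is completed at the first baseline visit and the envelope is opened after pre-test, so a further rule on that order would add little.
- **Covariate adjustment.** Section 14.0 plans to adjust for observed group differences, including vocational history. That offsets part of any measured selection but none of the unmeasured part, such as motivation that the recorded variables do not capture.

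These points reduce the size of the concern. They do not supply the missing custodian or justify printing a single block size.

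**Conclusion.** The concern holds as an avoidable opportunity for selection bias. One published block size, combined with overlap between recruitment and VR delivery within one staff group, allows up to 25% of allocations to be certain and 68% to be guessed at envelope opening. Both figures assume one unstratified 1:1 sequence, known block boundaries and complete knowledge of earlier assignments. If each location had its own list, the same share would apply within each list. The difference between the 160 and 180 totals changes the count, not the percentage.

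The documents do not show that anyone predicted an assignment or acted on a prediction, and the bias figures above are illustrative only. The change is worth making because it is cheap. It is a desirable improvement and not a condition for the trial's validity.

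**What to change.** For envelopes not yet opened:

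1. The statistician regenerates the remaining list with randomly varying block sizes, for example 4/6/8 or 6/8/10, which brings certain allocations down to about 2%.
2. Block sizes are removed from any document that recruiting staff can see and kept in a restricted statistical file. D.4 would then say only that permuted blocks of varying size are used.
3. D.4 names existing coordinating staff who neither recruit nor deliver VR, for example at Northwestern, which section 5.0 makes responsible for coordination. They hold and open the envelopes and, where feasible, keep the running allocation list from recruiters. This step is needed as well as the first, because varied block sizes alone leave best-guess success at about 66-70%.

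The plan was already in operation by the note of 1/29/18, and the documents do not say how many envelopes remain. If none do, the report should state who held the envelopes and who knew earlier assignments, and should compare baseline characteristics by position in block.

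**Cost.** A few hours of statistician time, a new set of envelopes, and a short contact with the custodian at each randomization. The final imbalance can reach half of the largest block, 4 or 5 clients for these mixes against 3 now. If the change comes in the middle of a block of six, up to 3 more are possible. Either has little effect on power.

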# D. 6. Visit 10 (Post-test Visit completed at Northwestern University, at a Threshold's Odgen location, or via a phone call or video-conference) will be a repeat of the following measures (see D.2. and D.3. for more details):

- 1. Brief Psychiatric Rating Scale (BPRS)
- 2. Beck Depression Inventory (BDI)
  - a. Columbia-Suicide Severity Rating Scale (C-SSRS) if triggered by BDI scores
- 3. Job-Interview Role Plays
- 4. Social Skills Performance Assessment(SSPA)
- 5. Employment History Interview (follow-up version)
- 6. Job Interview Self-Efficacy
- 7. Personal Report of Job Interview Anxiety
- 8. Intrinsic Motivation Inventory
- 9. Technology Comfort Level Questionnaire is a 6-item measure that assesses one's comfort level with computer technology (approximately 5 minutes).

In addition, VR trainees will complete the 5 item Training Experience Questionnaire (TEQ; < 5 minutes). The

Posttest Visit 10 will last approximately 150 minutes or 2 hours and 30 minutes. Participants will be paid \$50.

**D. 7. Monthly Check-in Telephone Calls for Thresholds Clients (completed via telephone) will involve a brief (<10minutes) telephone survey asking about participants' potential interview or job-related activity in the past month.** These calls will be scheduled at monthly intervals after completion of post-test until the 6-Month Follow-Up (see D. 9.), for a total of 5 calls.

D. 8. Visit 11 (6-Month Follow-Up Visit completed at Northwestern University, a Threshold's Ogden location or via a phone call or video-conference) will be a repeat of the following measures (see D.2. and D.3. for more details):

- 1. Brief Psychiatric Rating Scale (BPRS)
- 2. AUDIT-SR
- 3. DAST-10
- 4. WHOQOL-BREF
- 5. SF-36
- 6. Beck Depression Inventory
  - a. Columbia-Suicide Severity Rating Scale (C-SSRS) if triggered by BDI scores
- 7. Employment History Interview (follow-up version)
- 8. Job Interview Self-Efficacy
- 9. Personal Report of Job Interview Anxiety
- 10. Intrinsic Motivation Inventory

Participants will also complete the SF-12 health questionnaire about their physical health and the Employment History Follow-up interview that will assess how many job interviews were completed, total hours worked, how many jobs were offered (and accepted), hourly wage, type of job, jobs terminated (and why).

The 6-Month Follow-Up Visit 11 will last approximately 90 minutes or 1 hour and 30 minutes. Participants will be paid \$40. If the participant completed at least 3 of the 5 calls before the 6-Month Follow-Up visit, they will receive a \$10 bonus.

Follow-Up Visit 10 and Visit 11 scheduling protocol.

1. Study Participants' 6-month Follow-up visit (V11) will be scheduled 2-4 weeks before their due date. Scheduling will depend on the following:

a. If a participant is engaging in the monthly employment calls, their V11 will be scheduled at the time of their 5-month employment call.

b. If a participant is NOT engaging in the monthly employment calls, staff will contact the participant 4 weeks before the V11 due date. The contact process will be to use the phone to call the participant up to three times per week (only one time per day). Given that this population is difficult to reach, we will follow-up this initial phone call with an email and text message (for those participants who identified on their consent form that we can contact them by phone or emai.

2. If the study participant's V11 has not been scheduled by 2 weeks before their due date, staff will reach out to the participant's employment specialist and primary clinician for support contacting the participant.

3. If the study participant's V11 has not been scheduled by the time of their due date, staff will send a letter to the participant. The letter will explain the nature of the visit, the length of time the visit will take, and the staff person they should contact to schedule.

4. If the study participant does not respond to the letter or if their V11 is not scheduled by 6 weeks past their

due-date, staff will pull any available information from the electronic health record, and the member's study participation will end.

The same process will be used for scheduling Visit 10 as well.

Our primary method to collect Visit 10 and Visit 11 study data will be to invite participants to complete the visits at their local Thresholds location or Northwestern (as is the same for all in person study visits).

Alternatively, if participants are unable to attend visit 10 and/or 11 in person, the study team will schedule a series of brief phone calls in order to collect the self-reported study data by phone. In addition, the study team will offer participants the opportunity to complete their follow-up role-play assessment by means of a videoconference through BlueJeans. The BlueJeans videoconference will then be recorded by the University of Michigan research team that is approved for this study and the recordings will be stored using the previously approved methods for storing audiovisual data.

Alternatively, if the participants do not want to complete the videoconference then the participants will be offered the opportunity to complete their follow-up role-play assessment by means of a teleconference through BlueJeans. The BlueJeans teleconference will then be recorded by the University of Michigan research team that is approved for this study and the recordings will be stored using the previously approved methods for storing audiovisual data.

**D. 9. Monthly Check-in Telephone Calls for Thresholds Clients (completed via telephone) will be a repeat of procedures of the Monthly Check-in Telephone Calls for Thresholds Clients (see D. 8.).** These calls will be scheduled at monthly intervals after completion of the 6-month follow-up until the 9-month follow-up (see D. 11.), for a total of 2 calls.

D. 10. The 9-Month Follow-Up for Thresholds Clients (completed via telephone) will include only the Follow-up Employment History interview that will assess how many job interviews were completed, total hours worked, how many jobs were offered (and accepted), hourly wage, type of job, jobs terminated (and why).

The 9-Month Follow-Up Telephone Call will last approximately 10 minutes. If participants complete at least one of the two check-in calls between the 6-Month and 9-Month Follow-Up calls, they will be paid \$10 by Thresholds after the completion of the 9-Month Follow-Up call.

**D. 11. Participation Complete.** If a Thresholds client becomes employed prior to the 6-month follow-up call, they will still participate in monthly check-in phone calls and the 6-month follow-up. Their participation in the study will then be complete after completing the 6 month visit.

If the participant becomes employed between the 6- and 9-month follow-up calls, the participant will be asked additional questions on their next check-in call, which will be their last check-in.

For the Thresholds clients who do not find employment during before this time, participation is complete for this study after finishing their 9-Month Follow-Up Telephone Call.

**E. 1. Level 1.** The first level for the process evaluation of VR includes two pre-study implementation evaluations. The first is a 12-item Implementation Leadership Scale (<5 min) to evaluate the perspective of implementing evidence-based practice. The Thresholds Supported Employment Leadership team will complete this brief survey prior to conducting the RCT.

**E. 2. Level 2.** The second level for the process evaluation of VR will take place after approximately 30 VR trainees completed their work with VR and will include a series of 2-4 focus groups (consisting of 4-6 research participants per group) with existing research participants using VR. The groups will assess perceptions of initial VR implementation, with results guiding immediate modifications to VR delivery. The focus groups will be video-recorded and last approximately 60 minutes. Video-recording is required for participation in the focus groups. Each participant will be paid \$20 for their time. The focus groups will be led by research staff and conducted at Thresholds. The participation in focus groups is a one-time experience. See attached list of questions guiding the focus group.

In addition, Level 2 will consist of recruiting Team Leaders and Employment Specialists to complete the 26item Implementation Survey for Providers (<10 min).

**E. 2. Level 3.** The third level for the process evaluation of VR will take place after approximately 60 VR trainees completed their work with VR and will include conducting focus groups with Employment Specialists and Team Leaders involved with the study to complete 1-3 focus groups (consisting of 4-6 Thresholds Staff). The groups will target a discussion around client, service, and implementation outcomes. The focus groups will be video-recorded and last approximately 60 minutes. Video-recording is required for participation in the focus groups... The focus groups will be led by research staff and conducted at Thresholds. The participation in focus groups is a one-time experience. See attached list of questioning guiding the focus group.

**E. 3. Level 4.** After 6 months after VR delivery is completed, the Thresholds Supported Employment Leadership will be invited to complete the 31-item Annual Survey of Evidence-Based Practice (<15 min). This survey will assess the likelihood that Thresholds can sustain their use of VR after the study has ended.

**E. 3. Level 5.** Thresholds requires Employment Specialists (staff working one on one with clients on vocational rehabilitation) and Team Leaders (staff that orient clients to use VR) to document their weekly hourly activity logs, which will be copied and provided to the research team for the duration of the Thresholds' involvement in the study. Thresholds will provide the research team with activity logs for the 8 weeks prior to the beginning of the study. This data will help us evaluate how the allocation of person hours changes as a result of using VR, and in turn, will inform the cost effectiveness of VR. The activity log is attached to the IRB application. The logs will be anonymous to the study team, but will included a personal identification number so that the logs for the 8 weeks prior to the study can be compared to the logs collected once the study begins. The research team at Thresholds and Northwestern will not have access to the personal information of the Thresholds staff connected to these logs.

